### **Study Procedures**

After an eligible COVID-19 patient on supplemental oxygen has been identified, the research coordinator will contact patient via HIPPA compliant communication technology. The study will be verbally explained in detail with the patient. At time of verbal consent, instruction on use of the device will be performed by research team. If the patient progresses to meet the inclusion criteria and is enrolled in the trial, baseline metrics as above will be recorded. Patients will be provided a GO2 mouthpiece to be used in conjunction with and oxygen delivery face mask set to deliver an equivalent FIO2 to their previous therapy. **All patients will be instructed to breathe slowly and deeply through the mouthpiece for 15 minutes total.** Metrics for primary and secondary endpoints will be recorded before and after use of the mouthpiece (immediately prior to use and then at 5, 10 and 15 minutes of use and then 15 minutes after cessation of use).

Any decline in patient condition will result in immediate removal of the GO2 PEEP MOUTHPIECE and further appropriate care by the critical care team.

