### **Requirements**

We are seeking a rapid evaluation of the safety, efficacy, and feasibility of the device in patients with COVID-19 and pulmonary compromise. In order to test the performance of the device, we would identify a cohort of patients with a diagnosis of COVID-19. This cohort would be

characterized as those who require supportive care with supplemental oxygen but for whom ventilator support is not yet indicated or available. Once the patient is identified, consents to the study, and progresses to meet inclusion criteria based on oxygen requirements (>6L NC), then baseline measurements of oxygen saturation, respiratory rate, heart rate, blood pressure and blood gas results (when available) would be recorded. Furthermore, perceived effort of respiration would be measured including stridor, grunting, nasal flaring, or accessory muscle use. Patients would then be given the GO2 PEEP MOUTHPIECE for use in conjunction with oxygen therapy. Metrics would be recorded prior to initiation of therapy, 5, 10 and 15 minutes after GO2 PEEP therapy and 15 minutes after cessation of therapy.

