### **Research Design and Methods**

#### *Design*

This study will utilize a single center, single arm, pilot study design.

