#### *Inclusion Criteria*

- 1) COVID-19 positive
- 2) Oxygen saturation  $\leq 92\%$
- 3) Able to provide informed consent
- 4) Receiving oxygen  $\geq 6\text{L}$  nasal cannula
- 5) Not currently requiring intubation

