### **Study Endpoints**

#### *Primary Endpoint*

Improved oxygen saturation by pulse oximetry after treatment with the GO2 PEEP MOUTHPIECE.

The secondary endpoints include:

1. Respiratory rate
2. Heart rate
3. Blood pressure
4. Subjective work of breathing
5. Arterial blood gases (if available)

Both primary and secondary endpoints will be used to evaluate the safety as well as the efficacy of the GO2 PEEP MOUTHPIECE.

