## Statistical Analysis Plan

As an emergent COVID-19 study, our goal is to examine the safety, feasibility and efficacy of adding the GO2 PEEP MOUTHPIECE to COVID-19 patients already on oxygen therapy.

We will assess safety, feasibility and efficacy by observation of changes in the primary and secondary endpoints. At the conclusion of the study, we will assess metrics before and after application of the GO2 PEEP MOUTHPIECE, but given the few number of patients and low power of this initial study, statistical significance is not the focus of the analysis. However, we plan to provide statistical summaries that would be useful in a possible subsequent study, such as overall efficacy of the device and patterns and trends in primary and secondary endpoints.

Summary statistics on oxygen saturation (primary endpoint) and respiratory rate, heart rate, blood pressure, subjective work of breathing, and arterial blood gases as available (secondary endpoints) will be reported at each measurement occasion for each patient.

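### SpO2 is both entry cut-off and primary endpoint in a single-arm before/after design, so the change from one pre-use reading can include some regression to the mean; naming a contrast with readings already scheduled would reduce it

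*Combined protocol and SAP*

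**What the plan says.** Inclusion Criteria sets an upper limit of 92% on oxygen saturation. It does not say whether the qualifying value must be confirmed. The primary endpoint uses the same variable: "Improved oxygen saturation by pulse oximetry after treatment with the GO2 PEEP MOUTHPIECE". No comparator reading, time point or size of improvement is attached to it. On control, the Design section states: "This study will utilize a single center, single arm, pilot study design".

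On the order of events, Requirements describes a consented patient who "progresses to meet inclusion criteria based on oxygen requirements (>6L NC), then baseline measurements of oxygen saturation" and other vital signs are recorded. Study Procedures gives the same order: "If the patient progresses to meet the inclusion criteria and is enrolled in the trial, baseline metrics as above will be recorded". The readings are timed as "immediately prior to use and then at 5, 10 and 15 minutes of use and then 15 minutes after cessation of use". That makes one pre-use value, three on-device values and one off-device value.

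In the Statistical Analysis Plan, "we will assess metrics before and after application of the GO2 PEEP MOUTHPIECE" is the only comparison named. Summaries "will be reported at each measurement occasion for each patient", so the off-device value will be displayed, but it is given no role as a comparator. The SAP plays down significance testing, yet it intends to summarise efficacy for use in a possible later study. General Design Limitations mentions the variable course and unknown progression of the disease, not regression to the mean.

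**The concern.** When patients are selected because a variable reads low, and the same variable is then compared with one reading near the time of selection, the expected change is upward even if treatment does nothing. The bias has the same sign as the claimed benefit, and a single-arm study has no concurrent group in which to see it. Since no minimum improvement is set, a small spurious rise would count as improvement. The SAP's efficacy summary may also be carried into the planning of a later trial.

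The schedule already contains a partial remedy, the reading 15 minutes after cessation, but the plan names no contrast that uses it.

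**Working it through.** There is no stated figure to reproduce. The sample size of 5 comes without an effect size, SD, alpha or power. The check therefore asks how large a spurious rise could be with zero device effect, and how much of it a contrast using the off-device reading would remove.

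**Inputs from the documents:** cut-off 92%; on-device reading at minute 15; off-device reading at minute 30 (15 + 15); one pre-use reading.

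**Assumptions, because the documents give none of these:** each patient has a stable mean; patient means have SD 2; readings fluctuate around the patient's mean with SD 1 to 2; the correlation of fluctuations decays as exp(−t/τ).

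**Step 1: share removed.** Let D be the expected depth below the patient's own mean at the pre-use reading, r = exp(−15/τ) and x = 1 − r. Expected deviations at minutes 0, 15 and 30 are −D, −Dr and −Dr². Hence:

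- on-device minus pre-use: D(1 − r) = Dx
- on-device minus off-device: −Dr(1 − r) = −Dx(1 − x)
- on-device minus mean of pre-use and off-device: D(1 − r)²/2 = Dx²/2

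Relative to the simple change, the off-device reading alone removes a share x and leaves a remainder of opposite sign. The average removes 1 − x/2, which exceeds one half for every τ.

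| τ (min) | x | Removed, off-device alone | Removed, mean of pre-use and off-device |
|---|---|---|---|
| 5 | 0.950 | 95% | 52% |
| 15 | 0.632 | 63% | 68% |
| 30 | 0.393 | 39% | 80% |
| 60 | 0.221 | 22% | 89% |

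**Step 2: size without separate reading error.** With population mean μ, within-patient SD σ and s = √(2² + σ²), the expected depth at the qualifying reading is D₀ = (σ²/s)·φ(z)/Φ(z), where z = (92 − μ)/s. After a gap g, D = D₀·exp(−g/τ).

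Example with μ = 94, σ = 2, τ = 10: s = 2.83, z = −0.71, D₀ = 1.414 × 0.311/0.240 = 1.83, and x = 0.777.

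- Qualifying reading used as baseline: 1.83 × 0.777 = 1.42 points.
- Fresh reading 5 minutes later: 1.83 × 0.607 × 0.777 = 0.86 points.

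With μ = 90 instead, D₀ = 1.414 × 0.311/0.760 = 0.58, and the 5-minute case is 0.58 × 0.607 × 0.777 = 0.27 points.

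Over μ of 92 to 94, σ of 1 to 2 and τ of 10 to 40 minutes, the ranges are 0.11 to 1.42 (qualifying reading as baseline), 0.10 to 0.86 (5-minute gap) and 0.06 to 0.46 (15-minute gap). At μ = 88 they are at most 0.11 (5 minutes) and 0.06 (15 minutes).

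**Step 3: simulation with independent reading error (SD 1) added**, μ of 90 to 94, σ of 1 to 2, τ of 5 to 60 minutes, no device effect.

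| Baseline | Spurious mean rise at 15 min (points) | Patients rising |
|---|---|---|
| New reading 2 min after qualifying | 0.03 to 1.08 | 51–64% |
| New reading 30 min after qualifying | about 0 to 0.22 | 50–55% |
| Qualifying reading itself | 0.18 to 2.05 | 55–77% |

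With the averaged comparator, the residual is about 0 to 0.51 in the first two rows and 0.08 to 1.00 in the third. At the top of the third row the share removed is 1 − 1.00/2.05 = 51%.

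**The case against.** A reader might infer that patients are enrolled in a trough, just as saturation falls. The documents do not say so. Requirements ties progression to the oxygen requirement, and 92% is a ceiling, not a required drop. A patient who sits stably well below it qualifies with little regression to come.

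A reader might also infer that the baseline is the qualifying reading or is taken straight after it. Study Procedures places baseline after enrolment and immediately before use, and Protection of Human Subjects has the mouthpiece brought in by healthcare staff once the patient is enrolled. The natural reading is a fresh value after an unstated interval. A fresh value removes regression due to independent reading error and leaves only a dip that persists. The text does not explicitly exclude the qualifying value, but the largest figures depend on that less natural reading.

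Thirdly, a reader might infer that the off-device reading alone would remove most of the bias. It removes 39% at τ = 30 minutes and 22% at τ = 60, and over-corrects the remainder. The 52% to 89% belongs to the average with the pre-use reading.

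The other side can add that the assumed means drive the size, and that patients who are worsening would drift against the device. With five patients, the standard error of the mean change in the Step 2 model is 0.35 to 1.1 points, and with a fresh baseline the bias is below it in every case examined. The study is openly descriptive, and any reader of the five patients' listings could form the contrast.

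All of this limits the size and the urgency. It does not remove the selection on the endpoint variable, the lack of a control, or the absence of a named contrast from an analysis that intends to summarise efficacy.

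**Conclusion.** The point holds in a limited form. A before/after change in SpO2 from one pre-use reading can contain regression to the mean in the device's favour. With a fresh pre-use reading the likely range is about 0 to 1 point, and near 0 if the gap is long or patients are stably well below 92%. About 1.4 to 2 points arises only if the qualifying reading were used as baseline. The documents do not support saying that a device without effect would reliably appear to work: with a fresh baseline, 50% to 64% of patients rise in the simulations, against 50% by chance.

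These sizes rest on assumed SDs, population means and correlation times, and on stable patient means. The share removed by the averaged comparator also assumes exponential decay of correlation and no device effect left at the post-cessation reading. This is a cheap improvement to a descriptive pilot, not a flaw that invalidates it.

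**What to change.** - **Study Procedures:** state that the pre-use SpO2 is a new reading, distinct from the one that established eligibility. Repeat pre-use readings are optional.
- **Statistical Analysis Plan:** for each patient, report the simple change from the pre-use reading and, beside it, the 15-minute on-device SpO2 minus the mean of the pre-use and 15-minute post-cessation readings. These two readings fall at minutes 0 and 30 and average to minute 15, so the contrast also cancels a steady linear drift in either direction.
- **General Design Limitations:** list regression to the mean.

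The cost is wording. The contrast uses readings already scheduled, and the sample size does not change. The downside is carry-over: if benefit persists 15 minutes after removal, the second contrast understates it. Showing both summaries makes that visible.

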## Schedule of Assessments

Study Procedures	Prior to treatment with the mouthpiece	5 mins after PEEP therapy	10 mins after PEEP therapy	15 mins after PEEP therapy	15 minutes of after cessation of PEEP therapy
Consent	X				
Oxygen saturation	X	X	X	X	X
Respiratory rate	X	X	X	X	X
Heart rate	X	X	X	X	X
Blood pressure	X	X	X	X	X
Work of breathing 	X	X	X	X	X
Arterial blood gases (if available)	X			X	
Adverse events	X	X	X	X	X

 presence of any of the following: stridor, grunting, nasal flaring, or accessory muscle use

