## **Protection of Human Subjects**

### *Institutional Review Board (IRB) Review and Informed Consent*

Screening and enrollment will not begin until the Emory University IRB has approved the study protocol and informed consent form.

A physician investigator or study team designee(s) will obtain the informed consent via HIPPA compliant communication technology. A physician-investigator or study team member designee(s) will begin the verbal informed consent process with the subject with a diagnosis of COVID-19 infection. The nature of this infection precludes the research team from obtaining written consent before admission or in-person once the patient is admitted due to possible COVID-19 exposure and the handling of contaminated documents/pens. According to Emory critical care physicians, research staff are not permitted to enter COVID + rooms.

All COVID-19 positive patients will be screened for potential participation in the study. For the patients located in a telemetry unit or medical floor, a member of the research team will contact the patient remotely via phone (landline or via HIPAA compliant telehealth) to obtain verbal consent and give instruction on use of the device. Should the patient already be located in the ICU, and is unable to use the phone, the investigator will obtain consent via eICU. The patient must verbalize understanding of the consent before he/she consents. The subject's verbal consent will be obtained before any research related procedures are performed.

Once the patient meets inclusion criteria and is enrolled in the study, the investigator is responsible for getting the mouthpiece to the patient via healthcare staff. During the actual 15 minutes that the patient is using the GO2 PEEP MOUTHPIECE, the investigator will be able to monitor and communicate with the patient via eICU. The patient will also be able to communicate/view the investigator as well. The investigator will be able to collect all data remotely during this period.

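### The pre-use SpO2 reading is not tied to an oxygen interface, so the primary before/after change can include the cannula-to-mask switch

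*Combined protocol and SAP*

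**What the plan says.** Patients enter on cannula oxygen (Inclusion Criteria: "Receiving oxygen $\geq 6\text{L}$ nasal cannula") with a saturation of 92% or lower. Under Study Procedures they then use the mouthpiece together with a face mask adjusted to match the FIO2 of their previous therapy.

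The plan describes the reading before use in four places:

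- Study Procedures, on enrolment: "If the patient progresses to meet the inclusion criteria and is enrolled in the trial, baseline metrics as above will be recorded". The sentence that supplies the mouthpiece and mask comes next.
- Study Procedures, for the endpoint metrics: "immediately prior to use and then at 5, 10 and 15 minutes of use and then 15 minutes after cessation of use".
- Requirements, where baseline measurements come first and then: "Patients would then be given the GO2 PEEP MOUTHPIECE for use in conjunction with oxygen therapy". The same section adds: "Metrics would be recorded prior to initiation of therapy, 5, 10 and 15 minutes after GO2 PEEP therapy".
- Schedule of Assessments, in a single pre-use column: "Prior to treatment with the mouthpiece".

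The consent section describes a delivery step after enrolment, carried out by hospital personnel: "Once the patient meets inclusion criteria and is enrolled in the study, the investigator is responsible for getting the mouthpiece to the patient via healthcare".

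The primary endpoint is improved SpO2 after treatment, with no reference reading named. The Statistical Analysis Plan compares metrics before and after application and reports each occasion for each patient. No section states the oxygen interface for the pre-use reading or for the one 15 minutes after cessation. None gives the time allowed between qualifying and use.

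**The concern.** Two things change when the patient starts the session: the mouthpiece goes in, and oxygen moves from cannula to mask. A before/after difference isolates the first only if the reference reading is already on the mask. The plan does not require that. In a single-arm study no comparison group carries the mask switch without the mouthpiece, and five patients are too few to average out differences in how each was handled.

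A second, weaker issue is that the baseline metrics mentioned at enrolment may or may not be the reading taken just before use. If an earlier value were charted in the single pre-use column, the change could also contain recovery after a low qualifying SpO2, because eligibility is set on the endpoint variable itself.

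The stake is interpretation. The Statistical Analysis Plan intends summaries of the device's overall efficacy to inform a possible later study, and a change that includes the interface switch would carry over into its planning.

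**Working it through.** The plan gives no SD, expected effect, alpha or power, and its sample size of 5 is not derived, so there is no figure to reproduce. The check sets out what each possible reference reading leaves in the change, then sizes the unwanted parts under stated assumptions.

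**1. What the change contains.** Let D be the effect of mouthpiece use, M the SpO2 shift from cannula to mask, and R the recovery between qualifying and use. The expected change to 15 minutes of use is:

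- reference just before use, on the mask: D
- reference just before use, on the cannula: D + M
- reference at enrolment, on the cannula: D + M + R

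M is removed only by the first choice. Fixing the time alone does not remove it. The wording in Study Procedures fits the first and the second equally well.

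**2. Size of M (illustration).** Matching FIO2 makes M zero if the match is exact, but no section says how the match is checked. Assume a true FIO2 of 0.40 to 0.50, a mask setting off by 0.05, PaO2 proportional to FIO2, and a standard dissociation equation, S = 1 / (23400/(P³ + 150P) + 1). Setting S = 0.92 gives P = 63.8 mmHg.

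- 0.40 to 0.45: P = 63.8 × 1.125 = 71.8, S = 94.2%, M = +2.2 points
- 0.50 to 0.55: P = 63.8 × 1.100 = 70.2, S = 93.8%, M = +1.8 points
- 0.40 to 0.35: P = 63.8 × 0.875 = 55.8, S = 88.6%, M = −3.4 points
- 0.50 to 0.45: P = 63.8 × 0.900 = 57.4, S = 89.4%, M = −2.6 points

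The sign follows the direction of the mismatch, so the error can inflate or hide a benefit.

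**3. Size of R (illustration).** Assume that the qualifying reading itself is reused as baseline, with no device effect, patient means distributed N(m, s_b²) and independent reading error with SD s_w. Write s = √(s_b² + s_w²) and z = (92 − m)/s. The expected rise is (s_w²/s) × φ(z)/Φ(z).

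- m = 92, s_b = 3, s_w = 0.5: s = 3.04, z = 0, rise = 0.082 × 0.798 = 0.07
- m = 93, s_b = 2, s_w = 1: s = 2.24, z = −0.45, rise = 0.447 × 1.10 = 0.49
- m = 94, s_b = 1.5, s_w = 2: s = 2.5, z = −0.8, rise = 1.6 × 1.37 = 2.19

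Simulation over m = 92 to 94, s_b = 1.5 to 3 and s_w = 0.5 to 2 gave 0.06 to 2.19 points. With a fresh reading before use, the mean rise was about 0.

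A second simulation let SpO2 drift with a correlation time of 15 to 60 minutes, with a delivery delay of 15 to 60 minutes. It gave rises of 0.2 to 1.5 points from the qualifying reading and 0.0 to 0.35 from a reading just before use. None of these inputs comes from the documents.

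**The case against.** The strongest reply is that the endpoint baseline is already fixed. The one sentence that ties a pre-use reading to the endpoints times it immediately before use, the schedule has one pre-use column, and the enrolment sentence can be read simply as a condition that only enrolled patients get a baseline. This largely stands. A reader might infer that the plan sets two contradictory baselines. The documents do not support that: the enrolment sentence gives no clock time, and both wordings describe one reading if use follows at once. The consent section assigns delivery of the mouthpiece without placing the baseline before or after it. The figures for R therefore apply only if an enrolment or qualifying value is actually charted.

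The matched FIO2 is a real safeguard. It limits M, but the plan does not say how the match is verified.

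It is also true that no rule classifies a patient as improved, that significance is expressly not the focus, and that values are listed by occasion. This lowers the impact. The listing does not resolve the interface, however, because one pre-use column with no record of cannula or mask cannot show which was in use.

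**Conclusion.** The point holds in limited form. The reference reading for the primary SpO2 change is timed but not tied to an oxygen interface, and its relation to the enrolment baseline is not stated. If it is taken on the cannula, the change estimates device plus switch. Under a 0.05 FIO2 mismatch the switch part is about 2 to 3 points in either direction, and it is zero if the match is exact. Recovery after qualifying is an additional risk only if an earlier reading is used.

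A reader might infer a bias towards benefit. The documents do not support that, since M has no fixed sign and R is conditional. All sizes rest on assumed FIO2 values, SDs and delays. The change also includes the instructed slow, deep breathing and ordinary drift, which no choice of baseline removes in a single arm. For a descriptive study of five patients the impact is modest, so this is a cheap improvement.

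**What to change.** In Requirements, Study Procedures, the Schedule of Assessments and the Statistical Analysis Plan, name one reference reading for every change: the one immediately before use, taken with the study face mask already on at the plan's own matched-FIO2 setting and before the mouthpiece is placed.

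- Record the oxygen interface and clock time with every reading, including the one 15 minutes after cessation.
- Give any enrolment or cannula reading its own schedule column, list it as an eligibility value, and do not use it as the value before treatment.

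The cost is wording in four sections, one extra charted set of vital signs, and a short interval on the mask without the mouthpiece. That interval needs the clinical team's agreement. The oxygen setting and the clinical rules stay as written.

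### Body position is neither recorded nor matched across the five readings, so a change of position when use starts cannot be separated from a device effect on SpO2

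*Combined protocol and SAP*

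**What the plan says.** The Design section describes one arm at one center. Under Study Endpoints the primary endpoint is better pulse-oximetry saturation after treatment, with no size of change set. The Statistical Analysis Plan assesses efficacy by observing how the endpoints change before and after application. It reports values per patient at each occasion, along with summaries meant to inform a possible later study.

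Study Procedures sets five readings per patient: "immediately prior to use and then at 5, 10 and 15 minutes of use and then 15 minutes after cessation of use". One reading is before use, three are on the device and one is after it.

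The section matches one condition between the pre-use state and the session, inspired oxygen: the face mask is to be "set to deliver an equivalent FIO"2 equal to that of the previous therapy. The instruction for the session covers breathing and duration: "All patients will be instructed to breathe slowly and deeply through the mouthpiece for 15 minutes total".

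Requirements lists what is taken at the start: "baseline measurements of oxygen saturation, respiratory rate, heart rate, blood pressure and blood gas results (when available) would be recorded", plus signs of respiratory effort. The Schedule of Assessments repeats these items. Its only observational item about the patient's breathing is work of breathing, defined as "presence of any of the following: stridor, grunting, nasal flaring, or accessory muscle use". No section of the supplied document mentions body position or posture, and General Design Limitations does not name it.

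**The concern.** In an uncontrolled before-after comparison, any other condition that changes when the device goes on is counted as part of the device's effect. The plan accepts this for inspired oxygen, which it matches. Body position is another condition that may affect SpO2, respiratory rate and work of breathing in a patient short of oxygen, and the plan neither matches nor records it.

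The gap cannot be closed later. If position was not written down at the time of each reading, no analysis can tell which comparisons were made in the same position. With five patients, each one carries a fifth of the mean.

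**Working it through.** **Figures in the plan.** The only relevant figure is the sample size of 5. It comes without an effect size, SD, alpha or power, so there is no calculation to reproduce.

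**Where position could have been covered.**

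| Section | What it fixes or records | Position? |
|---|---|---|
| Requirements | Vital signs, blood gas if available, respiratory effort | No |
| Study Endpoints | SpO2 and five secondary measures | No |
| Study Procedures | Reading times, inspired oxygen, breathing instruction | No |
| Schedule of Assessments | Consent, endpoints and adverse events by time point | No |
| Statistical Analysis Plan | Endpoint summaries by patient and occasion | No |
| General Design Limitations | Disease course and progression | No |

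**What each comparison estimates.** Let m be the patient's underlying SpO2, d the device effect, and p0, p1 and p2 the contribution of position before, during and after use. Drift, carry-over and measurement error are left out for simplicity.

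- Pre-use: m + p0
- On device: m + d + p1
- Post-cessation: m + p2

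On device minus pre-use = d + (p1 − p0). On device minus post-cessation = d + (p1 − p2).

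There are three simple cases:

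1. No change of position (p0 = p1 = p2): both comparisons give d.
2. The patient moves at the start and stays there (p1 = p2, different from p0): the first comparison is off by p1 − p0, but the second gives d.
3. The patient moves at the start and moves back (p2 = p0, different from p1): both comparisons give d + (p1 − p0). They agree with each other, and both are wrong by the same amount.

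Without a record of position, the analyst cannot tell which case applies.

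**Size, as an illustration.** The document gives no figure for the effect of position or for how many patients would move. Assume that k of the 5 patients move when use starts and that each move shifts SpO2 by b points, all in the same direction. The shift in the mean change is b × k / 5.

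| | k = 1 | k = 3 | k = 5 |
|---|---|---|---|
| b = 1 | 1 × 1/5 = 0.2 | 1 × 3/5 = 0.6 | 1 × 5/5 = 1.0 |
| b = 2 | 2 × 1/5 = 0.4 | 2 × 3/5 = 1.2 | 2 × 5/5 = 2.0 |
| b = 3 | 3 × 1/5 = 0.6 | 3 × 3/5 = 1.8 | 3 × 5/5 = 3.0 |

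The range is 0.2 to 3 points. The sign may be plus or minus, and moves in opposite directions would partly cancel in the mean. In the per-patient results, a patient who moves is off by the full b points.

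**The case against.** The strongest reply is that the plan says nothing to suggest that patients move. A reader might infer that patients will sit up for the session and lie back afterwards, so that an inert device would look effective. The document does not support this. It does not give the resting position, say that the mouthpiece needs a particular one, or say that patients revert within 15 minutes. Nor does it show that a move would raise SpO2; it could lower it and bias against the device. This stands, and the point is therefore conditional and has no stated direction.

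A reader might also infer from the remote-monitoring text that patients hold a different position only while watched. That text reads "During the actual 15 minutes that the patient is using the GO2 PEEP MOUTHPIECE, the investigator will be able to monitor and communicate". It states what is possible during use. It does not say that viewing is absent at the other readings or that it affects position, so nothing here rests on it.

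The first reading comes directly before use, and device instruction is given earlier, at consent, so the patient may already be settled. That is a fair reading, but the plan does not say it, and making it explicit is most of the fix.

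The medical record, from which the data are drawn, may note position. No section requires this at the reading times.

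Finally, this is a five-patient pilot that sets significance testing aside and has no threshold for success, so no false-positive probability can be attached to the gap. That also stands. The plan still intends to summarize how well the device works, and the gap bears on that summary. The change from cannula to mask and the instruction to breathe slowly and deeply are certain to coincide with the device. They are separate issues and weigh more than this one.

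**Conclusion.** The gap is real and its weight is modest. Efficacy rests on an uncontrolled within-patient change in SpO2, and position is neither matched nor recorded at any of the five readings. If position changes when use starts, the pre-use comparison is confounded. The post-cessation reading fails as a check only if the position has reverted by then; if the patient stays put, it remains a useful same-position comparison.

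The illustrated shift in the mean of 0.2 to 3 SpO2 points rests wholly on assumptions: 1 to 5 patients moving, 1 to 3 points each, all in one direction. It shows scale and is not an estimate of bias in this study. The point is a cheap improvement of low priority.

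**What to change.** - **Study Procedures:** take the reading immediately before use once the patient has settled in whatever position will be used for the session.
- **Schedule of Assessments:** add a body-position row, completed in all five columns.
- **Statistical Analysis Plan:** show position beside each patient's SpO2 values, and flag any comparison made across different positions.

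This sets the timing of one reading and adds a record. It does not prescribe a position or require one to be held; positioning remains a matter for the clinical team.

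The cost is a few minutes of settling before the first reading, one extra row on the form, and some flagged comparisons. Because research staff may not enter the rooms, bedside staff may have to help with settling and with noting position.
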